3.1 Overall study design

This is an open-label, single-center 2-cohort pilot study, as shown in Figure 4. All patients will receive LB therapy until evidence of progression, intolerable toxicities or withdrawal from the study.

3.2 Study population

Figure 4. Study Design

3.2.1 Patient population

Adult patients with locally advanced or metastatic BCC.

The study will accrue 12 patients with locally advanced or metastatic basal cell carcinoma who are naïve to Smoothened inhibitors (COHORT 1) and 12 patients are refractory or resistant to non-Sonidegib SI (COHORT 2). This is an exploratory descriptive study.

3.2.2 Inclusion and exclusion criteria

Patients must have baseline evaluations performed prior to the first dose of study drug and must me*et al*l inclusion and exclusion criteria. Results of all baseline evaluations, which assure that all inclusion and exclusion criteria have been satisfied, must be reviewed by the Principal Investigator or his/her designee prior to enrollment of that patient. In addition, the patient must be thoroughly informed about all aspects of the study, including the study visit schedule and required evaluations and all regulatory requirements for informed consent. The written informed consent must be obtained from the patient prior to enrollment.

3.2.2.1 Inclusion criteria

Patients eligible for enrollment into the treatment phase of this study **must meet all** of the following criteria:

- 1. Able to understand and sign informed consent
- 2. Age \geq 18 years
- 3. ECOG performance status ≤ 2
- 4. Patients with metastatic BCC, histologic confirmation of distant BCC metastasis
- 5. Patients with metastatic disease, target lesion must be measurable using CT or MRI
- 6. Patients with locally advanced BCC are required to have disease that is considered inoperable due to significant functional compromise or to have a medical contraindication to surgery
- 7. Patients with nevoid BCC syndrome (Gorlin syndrome) may enroll in this study but must meet the criteria for locally advanced or metastatic disease listed above
- 8. **COHORT 2 ONLY**: A Smoothened inhibitor must have been previously administered as monotherapy)
- 9. Adequate bone marrow function as shown by:
 - a. ANC $\geq 1.5 \times 109/L$,
 - b. Platelets $\geq 80 \text{ x} 109/\text{L}$,
 - c. Hb > 9 g/dL or values \ge LLN for site-specific lab
- 10. Total calcium (corrected for serum albumin) within normal limits (biphosphonate use for malignant hypercalcemia control is not allowed)
- 11. Magnesium \geq the lower limit of normal
- 12. Potassium within normal limits for the institution
- 13. Alanine aminotransferase (ALT) and aspartate aminotransferase (AST) within normal range (or \leq 3.0 x upper limit of normal (ULN) if liver metastases are present)
- 14. Serum bilirubin within normal range (or ≤ 1.5 x ULN if liver metastases are present; or total bilirubin ≤ 3.0 x ULN with direct bilirubin within normal range in patients with well-documented Gilbert Syndrome)
- 15. Serum creatinine ≤ 1.5 x ULN or 24-hour clearance ≥ 50 mL/min
- 16. Serum amylase < ULN
- 17. Serum lipase ≤ ULN

- 18. Fasting plasma glucose $\leq 120 \text{ mg/dL}$ (6.7 mmol/L)
- 19. Negative serum pregnancy test within 72 hours before starting study treatment in women with childbearing potential
- 20. INR < 2

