Table 6. Numbers of patients with liver toxicity occurred at 100 mg/day in ongoing buparlisib studies

Study Number (N = patient treated with 100 mg/d buparlisib)	All grades	Grade 3-4
CBKM120X2101 ($N = 55$)	22 (40%)	13 (23%)
CBKM120X1101 (N = 9)	4 (44%)	4 (44%)
CBKM120C2201 (N = 50)	10 (20%)	6 (12%)

CBKM120X2107 (N = 12)	2 (16%)	2 (16%)
CBEZ235A2118 (N = 6, buparlisib-treated only)	0 (0%)	0 (0%)

Based on these findings, conservative selection criteria and guidelines to monitor and to follow patients with LFT alterations (including dose and schedule modifications) are currently implemented in study protocols investigating buparlisib.

Mood alteration of Buparlisib

Recently, a number of publications demonstrated that the modulation of AKT/GSK3 signaling pathway by neurotransmitters is important for the regulation of behavior. Preclinical studies conducted in rats to investigate the effect of buparlisib on different neurotransmitters have shown that repeated administration of buparlisib resulted in an enhanced decrease in glutamate, dopamine, serotonin and epinephrine as well as in an enhanced increase in GABA and HIAA.

Reversible mild to moderate mood disorders observed at 100 mg/day, regardless of study drug relationship, in ongoing buparlisib studies are summarized in the Investigator's Brochure. (see also Table 7 below)

Table 7. Numbers of patients with mood disorders occurred at 100 mg/day in ongoing buparlisib studies

Study Number (N = patient treated with 100 mg/d buparlisib)	All grades	Grade 3-4
CBKM120X2101 (N = 55)	11 (20%)	2 (3%)
CBKM120X1101 (N = 9)	4 (44%)	0 (0%)
CBKM120C2201 (N = 50)	6 (12%)	0 (0%)
CBKM120X2107 (N = 12)	7 (58%)	2 (16.7%)
CBEZ235A2118 (N = 6, buparlisib-treated only)	0 (0%)	0 (0%)

These adverse events are currently under investigation. Nevertheless, until a more complete understanding of this AE is compiled and in order to lower the risk, protocol guidelines disqualify patients with an active and/or history of major psychiatric disorder. In addition, throughout the trial patients must be closely monitored using self-rating questionnaires (ie, PHQ-9 and GAD-7), when required a psychiatrist should be consulted and the use of standard available medication should be considered as per investigator's discretion.

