CTCAE Grade 3 or 4 CK elevation (with or without muscle pain/spasm)	 ♦♦ Omit sonidegib dose, check blood myoglobin and monitor renal function. Measure CK weekly until resolution to Grade ≤ 1 ♦♦ Consider performing electromyography, MRI scan of symptomatic muscle group(s) and muscle biopsy ♦♦ If renal function is not impaired and resolution to ≤ CTCAE Grade 1 occurs within 21 days, consider resuming treatment at a reduced dose; CK should be measured weekly for 2 months after readministration of sonidegib ♦♦ Patients who experience renal impairment (serum

creatinine > 2x ULN) should be permanently
discontinued from the study
◆◆ If a Grade 4 event, consider hospitalization if
appropriate

Table 9. Recommended dose modifications and dose delays for suspected sonidegib** treatment-related toxicities	
Worst toxicity CTCAE grade* (value)	
Muscle pain/spasm (new onset or worsening of preexisting muscle pain/spasm)	 ♦♦ For CTCAE Grade 1 muscle pain/spasm, continue treatment on the same dose and planned assessments ♦♦ For CTCAE ≥ Grade 2 muscle pain/spasm, measure CK weekly until muscle pain resolves to ≤ Grade 1. If CK is elevated, follow guidance for CK elevation as described above. Continue treatment with sonidegib ♦♦ For new-onset CTCAE Grade 3 muscle pain/spasm, interrupt sonidegib. Collect blood sample for CK measurement at the time of dose interruption. Provide symptomatic treatment. Measure CK weekly until the muscle pain/spasm resolves to ≤ Grade 1 and resume therapy at a reduced dose. Measure CK weekly for 2 months after re-administration.
	Renal
	Serum creatinine
Serum creatinine <1.5 x ULN	Maintain dose level
Serum creatinine 1.5-3 x ULN	Omit dose until resolved to ≤ Grade 1, then: ◆ If resolved in ≤ 7 days, then maintain dose level • If resolved in > 7 days, then implement 50% dose reduction (consider checking serum CK, if not already done)
Grade 3 Serum creatinine > 3.0 - 6.0 x ULN	Omit dose until resolved to ≤ Grade 1 then implement 50% dose reduction
Grade 4 Serum creatinine > 6.0 x ULN	Omit dose and discontinue study drug. Consider hospitalization if appropriate
	Hepatic
	Bilirubin
Total bilirubin <1.5 x ULN	Maintain dose level

Total bilirubin 1.5-3 x ULN	Omit dose until resolved to ≤ Grade 1, then: ♦ If resolved in ≤ 7 days, then maintain dose level ♦ If resolved in > 7 days, then implement 50% dose reduction
Grade 3 Total bilirubin > 3.0 - 10.0 x ULN	Omit dose until resolved to ≤ Grade 1, then implement 50% dose reduction

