If a patient requires a dose interruption of > 21 days from the intended day of the next scheduled dose because of a sonidegib-related toxicity, then the patient must be discontinued from the study.

*Common Toxicity Criteria for Adverse Events (CTCAE Version 4.0).

** If the investigator deems that a recommended dose reduction or the recommendation to maintain the same dose level is not in the best interest of the patient, this decision may be discussed with Novartis on a case-by-case basis.

Criteria for follow-up and dosing modifications for buparlisib are described in detail in Table 10.

For overlapping toxicities of sonidegib and buparlisib, specifically hematologic, renal and hepatic toxicities, BOTH sonidegib and buparlisib will be reduced or discontinued depending on toxicity grade per the guidelines listed below for each drug (Tables 9 and 10).

Table 10. Recommended dose modifications and dose delays for suspected buparlisib treatment-related toxicities		
Worst toxicity CTCAE grade* (value)	During a cycle of therapy	
	Hematologic	
]	Neutropenia (ANC)	
Grade 1 (ANC < LLN - 1500/mm ³)	Maintain dose level	
Grade 2 (ANC < 1500 - 1000/mm ³)	Maintain dose level	
Grade 3 or 4 (ANC < 1000 - 500/ mm ³ or < 500/mm ³)	 Omit dose until resolved to ≤ Grade 1, then: If resolved in ≤ 7 days, implement 50% dose reduction If resolved >7 days, discontinue drug If a Grade 4 event, consider hospitalization if appropriate 	
Thrombocytopena		
Grade 1 (PLT < LLN - 75 x 10 ⁹ /L)	Maintain dose level	
Grade 2 (PLT < 75 - 50 x 10 ⁹ /L)	Maintain dose level	

Grade 3 (PLT $< 50-25 \times 10^9/L$)	Omit dose until resolved to ≤ Grade 1, then:	
	 If resolved in ≤ 7 days, then maintain dose level If resolved in > 7 days, then implement 50% dose reduction 	
Grade 4 (PLT < 25 x 109/L)	Omit dose until resolved to ≤ Grade 1, then implement 50% dose reduction. Consider if hospitalization is appropriate	
	Renal	
	Serum creatinine	
Serum creatinine <1.5 x ULN	Maintain dose level	
Serum creatinine 1.5-3 x ULN	Omit dose until resolved to ≤ Grade 1, then: •• If resolved in ≤ 7 days, then maintain dose level •• If resolved in > 7 days, then implement 50% dose reduction (consider checking serum CK, if not already done)	
Table 10. Recommended dose modifications and dose delays for suspected buparlisib treatment-related toxicities		
Worst toxicity CTCAE grade* (value)	During a cycle of therapy	

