Grade 3 Serum creatinine > 3.0 - 6.0 x ULN	Omit dose until resolved to ≤ Grade 1 then implement 50% dose reduction	
Grade 4 Serum creatinine > 6.0 x ULN	Omit dose and discontinue study drug. Consider hospitalization if appropriate	
Hepatic		
Bilirubin (*for patients with Gilbert syndrome these dose modifications apply to changes in direct bilirubin only) will be fractionated if elevated		

Total bilirubin <1.5 x ULN	Maintain dose level
T . 1177 1: 150 IV	Omit dose until resolved to \leq Grade 1, then:
Total bilirubin 1.5-3 x ULN	◆◆ If resolved in ≤ 7 days, then maintain dose level
	◆◆ If resolved in > 7 days, then implement 50% dose
	reduction
Condo 2	Ourit dans until manhand to < Conda 1 than
Grade 3	Omit dose until resolved to ≤ Grade 1, then implement 50% dose reduction
Total bilirubin > 3.0 - 10.0 x ULN	implement 30% dose reduction
Grade 4	Discontinue study medication
Total bilirubin > 10.0 x ULN	Consider if hospitalization is appropriate
	AST or ALT
Grade 1 (> ULN - 3.0 x ULN)	
	Maintain dose level
Grade 2 (> 3.0 - 5.0 x ULN)	Maintain dose level
Grade 3 (> 5.0 - 20.0 x ULN)	Omit dose until resolved to < Grade 1 or baseline then:
	♦♦ If resolved in \leq 7 days, then maintain dose level
	◆◆ If resolved in > 7 days, then implement 50% dose
	reduction
Grade 4 (> 20.0 x	Discontinue study drug
ULN)	Consider if hospitalization is appropriate
AST or	ALT and concurrent Bilirubin
AST or ALT > 3.0 x ULN and	Discontinue study drug
total bilirubin > 2.0 x ULN	

*(LFTs include albumin, ALT, AST, total bilirubin (fractionated if total bilirubin > 2.0 x ULN), alkaline phosphatase (fractionated if alkaline phosphatase is Grade 2 or higher) and GGT). Monitoring (*for patients with Gilbert Syndrome: total and direct bilirubin must be monitored, intensified monitoring applies to changes in direct bilirubin only; the monitoring includes the following LFTs: albumin, ALT, AST, total bilirubin (fractionated if total bilirubin > 2.0 x ULN), alkaline phosphatase (fractionated if alkaline phosphatase is Grade 2 or higher) and GGT).

In case of any occurrence of ALT/AST/ bilirubin* increase ≥ **Grade 2** the liver function tests must be monitored **weekly** or more frequently if clinically indicated **until resolved to** ≤ **Grade 1**

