APPENDIX B: Participant Eligibility Checklist

Protocol Title:	An open-label pilot study to evaluate the efficacy and safety of a combination treatment of Sonidegib and buparlisib for the treatment of advanced basal cell carcinomas
Protocol Number:	IRB-29839
Principal Investigator:	[name]

II. Subject Information:

Subject Name/ID:

Gender: Male Female

III. Inclusion/Exclusion Criteria

Inclusion Criteria			Supporting
	Yes	No	Documentation*

1. Age 18 years or older.		
2. Able to provide written informed consent obtained prior to any screening procedures		
3. Histologically documented diagnosis of basal cell carcinoma deemed to be locally advanced or metastatic		
4. ECOG performance status ≤ 2		
5. At least one measurable site of disease (as defined by Response Evaluation Criteria in Solid Tumors), or other disease specific response assessment criteria, as appropriate.		
State age restriction and/or gender/race-ethnic restrictions.		
6. Patients with adequate bone marrow, liver and renal function, as specified below:		
• Absolute Neutrophil Count (ANC) ≥ 1.5 x 10 ⁹ /L		
• Hemoglobin (Hgb) ≥ 9 g/dL		
• Platelets $\geq 80 \times 10^9/L$		
• Serum total bilirubin ≤ 1.5 x ULN (upper limit of normal)		
• AST and ALT ≤ 2.5 x ULN or ≤ 5 x ULN if liver metastases are present		
• Plasma creatinine phosphokinase (CK) \leq 1.5 x ULN		
• Serum creatinine ≤ 1.5 x ULN or 24-hour clearance ≥ 50 mL/min		
◆◆ CK > ULN		

Exclusion Criteria	Yes	No	Supporting Documentation*

Cohort 1 only: prior therapy with non- Sonidegib Smo Inhibitor	
2. Patients who have received prior treatment with a P13K inhibitor	
3. Patients with a known hypersensitivity to buparlisib or to its excipients	
4. Metastatic CNS tumors may participate in this trial, if the patient is ≤ 4 weeks from therapy completion (incl. radiation and/or surgery), is clinically stable at the time of study entry and is not receiving corticosteroid therapy	
5. Patients who have had major surgery within 4 weeks of initiation of study medication.	
6. Patients with concurrent uncontrolled medical conditions that may interfere with their participation in the study or potentially affect the interpretation of the study data.	
7. Patients unable to take oral drugs or with lack of physical integrity of the upper gastrointestinal tract or known malabsorption syndromes. State exclusion requirements due to co-morbid disease or incurrent illness, as needed.	

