21. Patients who have undergone major surgery ≤ 2 weeks prior to starting study drug or who have not recovered from side effects of such therapy.	
22. Patients who are currently taking therapeutic doses of warfarin sodium or any other coumadin-derivative anticoagulant. Low molecular weight heparin is allowed.	
23. Known diagnosis of human immunodeficiency virus (HIV) infection, Hepatitis B or Hepatitis C	
24. History of another malignancy within 3 years, except cured basal cell carcinoma of the skin, cured squamous cell carcinoma of the skin or excised carcinoma in situ of the cervix	
 25. Patients with the following mood disorders as judged by the Investigator or a psychiatrist, or as a result of patient's mood assessment questionnaire: ♦♦ Medically documented history of or active major depressive episode, bipolar disorder (I or II), obsessive-compulsive disorder, schizophrenia, a history of suicidal attempt or ideation, or homicidal ideation (immediate risk of doing harm to others) ♦♦ ≥ CTCAE Grade 3 anxiety ♦♦ Meets the cut-off score of ≥ 12 in the PHQ-9 or a cut-off of ≥ 15 in the GAD-7 mood scale, respectively, or selects a positive response of "1, 2, or 3" to question number 9 regarding potential for suicidal thoughts in the PHQ-9 (independent of the total score of the PHQ-9) 	

26. Patients unwilling or unable to comply with the protocol.		
me presection		

IV. Statement of Eligibility

This subject is **eligible** / **ineligible** for participation in the study.

Signature:
Date:
Printed Name:

^{*}All subject files must include supporting documentation to confirm subject eligibility. The method of confirmation can include, but is not limited to, laboratory test results, radiology test results, subject self-report, and medical record review.

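### The Appendix B eligibility checklist sets one bilirubin limit (1.5 x ULN) that contradicts inclusion criterion 14: looser for patients with neither liver metastases nor Gilbert syndrome, stricter for Gilbert patients with normal direct bilirubin

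*Combined protocol and SAP*

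**What the plan says.** Section 3.2.2.1, criterion 14, opens with "Serum bilirubin within normal range (or ≤ 1.5 x ULN if liver metastases are present" and adds a third branch for Gilbert syndrome: "total bilirubin ≤ 3.0 x ULN with direct bilirubin within normal range in patients with well-documented Gilbert Syndrome". Section 3.2.2.1 requires every listed criterion to be met. Section 3.2.2 has the principal investigator or a designee review the baseline results against all criteria before enrolment.

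Appendix B, inclusion item 6, has a single bilirubin line: "Serum total bilirubin ≤ 1.5 x ULN (upper limit of normal". It has no branch for liver metastases or Gilbert syndrome and no condition on direct bilirubin. The next line of the same item, for AST and ALT, does have a liver-metastasis branch. The checklist ends with a signed and dated statement that the subject is eligible or ineligible, and a note that "All subject files must include supporting documentation to confirm subject eligibility".

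The documents do not say which text prevails where the two differ.

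**The concern.** The checklist is the form on which each patient is declared eligible. If its threshold differs from the protocol's, a site working from the form can enrol a patient the protocol bars or turn away one it admits. A site that checks both has two incompatible answers and no stated rule for choosing between them.

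The looser direction bears on safety. Section 1.5.2.2.1 says that, because of the liver findings, buparlisib protocols use "conservative selection criteria and guidelines to monitor and to follow patients with LFT alterations". A checklist that relaxes the default from the normal range to 1.5 x ULN works against that intention. The stricter direction could cost eligible patients in cohorts of only 12 each (Section 3.2.1).

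**Working it through.** No power or sample-size calculation is involved. The check sets the two thresholds side by side.

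Inputs: the three limits of criterion 14 (Section 3.2.2.1) and the one limit of Appendix B item 6. The normal range is read as total bilirubin up to 1.0 x ULN.

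| Patient group | Criterion 14, total bilirubin | Appendix B, total bilirubin | Band where they disagree |
|---|---|---|---|
| No liver metastases, no Gilbert | ≤ 1.0 x ULN | ≤ 1.5 x ULN | above 1.0 to 1.5: checklist line passes, criterion 14 bars |
| Liver metastases, no Gilbert | ≤ 1.5 x ULN | ≤ 1.5 x ULN | none |
| Gilbert, direct bilirubin normal | ≤ 3.0 x ULN | ≤ 1.5 x ULN | above 1.5 to 3.0: checklist line rejects, criterion 14 admits |
| Gilbert, direct bilirubin raised, no liver metastases | ≤ 1.0 x ULN (Gilbert branch fails, default applies) | ≤ 1.5 x ULN | above 1.0 to 1.5: checklist line passes, criterion 14 bars |

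In the third row the limits differ by a factor of 3.0 / 1.5 = 2. In the first and fourth rows the factor is 1.5 / 1.0 = 1.5, in the opposite direction. The conflict therefore cannot be resolved by calling one text simply the more cautious.

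Context for the strict default, from Table 6 (Section 1.5.2.2.1; buparlisib 100 mg/day; Grade 3-4 liver toxicity regardless of relationship):

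- Events: 13 + 4 + 6 + 2 + 0 = 25.
- Patients: 55 + 9 + 50 + 12 + 6 = 132.
- Pooled proportion: 25 / 132 = 18.9%.

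The same section says the liver-test changes were mostly transaminase rises, and this study gives 80 mg. The figure shows why selection was made conservative. It does not estimate the harm from admitting a patient at, say, 1.3 x ULN bilirubin.

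The documents give no baseline bilirubin distribution and no Gilbert prevalence, so the number of patients in each band cannot be derived.

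**The case against.** **The checklist does not stand alone.** Section 3.2.2 requires review against every criterion before enrolment. Appendix B has no line for calcium, magnesium, potassium, amylase, lipase, fasting glucose or INR, so it cannot replace Section 3.2.2.1, and a site using only the form would already be departing from the protocol. Liver disease is also excluded separately (Section 3.2.2.2 item 4; Appendix B exclusion 15), so passing the bilirubin line is not passing the whole checklist. This stands and lowers the practical risk. But neither exclusion contains a bilirubin threshold, and neither helps a Gilbert patient whom the form wrongly rejects.

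**The safety argument fits transaminases better than bilirubin.** This also stands in part, which is why the 18.9% serves only as background. The neighbouring AST/ALT line has a mismatch of its own: ≤ 2.5 x ULN, or ≤ 5 x ULN with liver metastases, against the normal range, or ≤ 3.0 x ULN with liver metastases, in criterion 13.

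**A reader might infer a second error in the dose rules.** The bilirubin rows of Table 10 (buparlisib) carry a note that "for patients with Gilbert syndrome these dose modifications apply to changes in direct bilirubin only". The rows of Table 9 (sonidegib), such as "Total bilirubin 1.5-3 x ULN", have no such note. Section 4.1 says that for overlapping hepatic toxicity "BOTH sonidegib and buparlisib will be reduced or discontinued depending on toxicity grade per the guidelines listed below for each drug". A Gilbert patient whose total bilirubin rises on treatment could then have sonidegib held and buparlisib continued. The documents do not show that this is a mistake:

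- The tables differ by drug elsewhere, for example on Grade 3-4 platelets and Grade 4 AST/ALT.
- Table 2 lists increased blood bilirubin (8 of 103, 7.8%) and hyperbilirubinaemia (6 of 103, 5.8%) among events suspected to be related to sonidegib, so a stricter rule for that drug is plausible.
- Table 9 is a set of recommendations for suspected sonidegib toxicity, and its footnote allows case-by-case discussion with the manufacturer.

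Nor do the documents support the further inference that a stable Gilbert baseline would by itself force sonidegib to be held and the patient withdrawn after 21 days. Pre-existing conditions count as adverse events only if they worsen (Section 4.3.4.1), and the investigator may attribute a value to another clearly identified cause (Section 4.3.3).

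**Conclusion.** The contradiction between criterion 14 and Appendix B item 6 holds on the text alone. It covers three bands: above 1.0 to 1.5 x ULN with neither liver metastases nor Gilbert syndrome; above 1.5 to 3.0 x ULN in Gilbert syndrome with normal direct bilirubin; and above 1.0 to 1.5 x ULN in Gilbert syndrome with raised direct bilirubin and no liver metastases. The limits agree for patients with liver metastases and no Gilbert syndrome.

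Severity is minor. The study is descriptive, no hypothesis test or stated figure depends on the threshold, and the safeguards above limit the risk. The conclusion assumes only that the normal range means up to 1.0 x ULN and that both texts are in force.

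The difference between Tables 9 and 10 is at most a question to the sponsor. It is not part of this finding.

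**What to change.** Replace the Appendix B bilirubin line with the full content of criterion 14: the default limit, the liver-metastasis limit, and the Gilbert limit with its condition that direct bilirubin be normal. This costs one line on a form. No new test is needed, because the serum chemistry panel in Section 4.3.5.2 already reports direct and indirect bilirubin.

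In the same edit, check the adjacent AST/ALT line against criterion 13, since correcting bilirubin alone leaves that mismatch in place.

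Separately, ask the sponsor whether the absence of a Gilbert note in Table 9 is intended. Do not copy the note across without that answer: it would loosen a sonidegib safety rule without support in the documents.
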